Heparin and lidocaine allergy: Both carry the potential risk of eliciting an allergic reaction. The risk of developing an allergic reaction to each of these individually or cumulatively is very small. Some symptoms of an allergic reaction include itching, tingling, chest tightness, difficulty breathing, nausea, or vomiting. Subjects will be continuously monitored for each of these symptoms. The **probability** of this risk is very low and **severity** of these risks is moderate.

Safety Equipment available in the Cardiopulmonary and Respiratory Physiology Laboratory where all testing and screening will be performed):
Phillips FRx AED, a spare AED battery, and spare AED pads.

Emergency Procedures: According to American Heart guidelines, in the event of an adverse cardiopulmonary event, we will begin CPR, call 911 (as directed by U of O EH&S), and will continue CPR as required until emergency medical personnel arrive.

Safety Monitoring: *Subjects will be given clear instructions that they should notify the investigators immediately if they experience any of the above-mentioned risk symptoms.* During all exercise and recovery procedures, all subjects will be non-invasively and continuously monitored for vital signs using: 1) a 12 lead EKG to monitor electrical activity of the heart, and 2) a forehead probe to monitor arterial oxygen saturation and heart rate. During all other procedures subjects will be visually monitored for any signs of discomfort, distress or problems. During both exercise and resting procedures, the investigators will continuously ask the subjects how they are feeling and how they are doing.

H. Potential Benefits of the Research

This study will not improve the health of subjects and is only being done to gather information. This study will not improve the health of the general subject population. Completing the aims of this study will have the benefit of contributing to generalizable knowledge.

I. Investigator Experience

The PI and colleagues have been performing cardiopulmonary and respiratory physiology investigations at rest and during exercise in healthy and diseased populations at the University of Oregon for ~10 years. [name] CV is on file.

The PI trains all graduate and undergraduate personnel on all laboratory procedures and protocols. Co-investigator [name] is a board certified cardiologist who has worked with [name] group for almost 10 years placing radial artery

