Does Patent Foramen Ovale Size Matter in Men and Women

NCT #: Not Assigned

Dec 12, 2018

Study Title: Does patent foramen ovale size matter in men and women?

Protocol Number: 04302018.049

Principal Investigator: [name]

A. Introduction and Background

A patent foramen ovale (PFO) is present in ~30% of the general population. The PFO has historically been considered to be trivial. However, recent work by our group and others has identified that, compared to individuals without a PFO, those with a PFO have worse pulmonary gas exchange efficiency, have a higher core body temperature, blunted ventilatory responses to chronic hypoxia and acute carbon dioxide and increased susceptibility to altitude illnesses such as acute mountain sickness, and high altitude pulmonary edema (Lovering, Elliott & Davis J Appl Physiol 2016). Specific to this application, subjects with a PFO may have worse pulmonary gas exchange efficiency because a PFO is a potential source of right-to-left shunt that will make pulmonary gas exchange efficiency worse. If true, then this may negatively impact exercise capacity and/or exercise tolerance.

Further, in those with a PFO compared to those without, preliminary work from our lab indicates that there may be an effect of PFO size on pulmonary gas exchange efficiency. This is such that those with a large PFO (grade 3 or higher) display significantly worse gas exchange efficiency compared to those with a small (grade 2 or lower) or no PFO, even at low exercise workloads. Additionally, we were curious as to whether there would be a sex effect, but due to logistical constraints, we were unable to recruit an equal number of female and male subjects. Thus, in addition to the potential size effect on our outcome measures, we would like to build on this work by examining the potential effect of biological sex.

Although a PFO has been traditionally considered to have a minimal impact of physiology and pathophysiology, emerging evidence suggests this may not be the case. Our lab is focused on understanding how and why a relatively small hole in the heart (PFO) can have a relatively large impact on cardiopulmonary and respiratory physiology, and how these impacts may be based on the size of the PFO.

B. Specific Aims/Study Objectives

The overarching goal of this study is to examine how cardiopulmonary and respiratory physiology may be altered by the size of a PFO and/or biological sex.

To do this, we will:

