- 1)** Quantify pulmonary gas exchange efficiency (alveolar to arterial O₂ difference) and arterial oxygenation at rest and during exercise.
- 2)** Quantify aerobic exercise capacity and six-minute walk test.
- 3)** Quantify Q_{IPAVA} at rest.
- 4)** Quantify plasma inflammatory markers (TNF α , IL-1, 6 & CRP)
- 5)** Quantify core body temperature

Hypotheses: We hypothesize that those individuals with a large PFO will display worse pulmonary gas exchange efficiency, compared to those with a small or no PFO; there will not be a sex effect. A large PFO, when compared to a small or no PFO, will be associated with increased plasma inflammatory mediators, and will result in a higher core body temperature.

C. Methods, Materials and Analysis

This study will be performed over the course of 3 days at the Cardiopulmonary and Respiratory Physiology Lab at the University of Oregon.

Screening at each study visit: Female subjects will be required to take a urine pregnancy test before each visit begins. A positive test at anytime will result in exclusion. A Modified Allen's test will be performed on Day 1 for all subjects and during the day when an arterial line is placed (Day 3). Failing the Modified Allen's test at anytime will result in exclusion.

Description of Study Days

Day 1 (~ 2 hours)

Subjects will undergo informed consent, fill out health history questionnaire, and perform a Modified Allen's Test (~45 min)

Subjects will be comprehensively screened for any cardiac abnormalities. Amount of blood flow travelling through the PFO and IPAVA will be graded using saline contrast echocardiography while the subject is breathing room air (PFO and IPAVA blood flow) and breathing 100% O₂ (PFO blood flow only). Pulmonary artery pressure will also be measured using ultrasound. Intravenous blood draw, we will take 21mls (~2 Tablespoons) of iv blood (~1.25 hrs)

Subjects will perform pulmonary function, plethysmography and diffusing capacity (30min)

Day 2 (~ 1 hour)

Subjects will perform a 6 minute walk test (~15 min)

Subjects will perform a VO2max test (~30 min)

Day 3 (~ 3.5 hours)

Subjects will be instrumented with a radial artery catheter by [name], MD. An esophageal temperature probe and an iv for saline contrast injections will also be placed. (~1hr)

Arterial blood will be taken at rest while subject is breathing room air and 100% O2 for 10-20 minutes to calculate shunt fraction (~30 min).

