Necessary sample size was determined with our primary outcome variables (AaDO₂, VO₂MAX, saline contrast bubble scores, TNF α levels) using our preliminary data, previously published work and *a priori* power analysis. Using G-Power and information about a physiologically-meaningful effect from published studies, we determined that n = 15 individuals would be sufficient to test our hypotheses. Thus, we are asking to recruit 45 subjects (sex of these subjects may be chosen specifically to ensure even distribution of subjects in order to appropriately analyze the effect of sex on our outcome measures) in the event our actual pre-to-post changes are less than expected and/or there is greater variability than our preliminary data suggest.

Mean differences in AaDO₂ and core body temperature between males and females, and between those with a small or no PFO compared to a large PFO will be analyzed

using a mixed analysis of covariance (MANCOVA). Mean differences in VO_{2MAX}, 6 minute walk test, inflammatory markers between males and females, and between those with a small or no PFO compared to a large PFO will be analyzed using an unpaired t-test.

The population of subjects will include males and females between the ages of 18-40 and will be recruited via subject fliers. In addition, subjects known to have or not have a PFO based on previous participation in studies in the Cardiopulmonary and Respiratory Physiology Lab at the University of Oregon may be contacted to evaluate whether they would be interested in participating in this study.

Subject fliers, initial phone script and email script are attached.

Detailed Recruitment Information

A) Once a subject contacts us (via flier) or is contacted by us (via previous study participation) we will use the phone script (attached) to determine their eligibility. The phone script is the first instance where the subject will be informed about restrictions regarding caffeine/alcohol/food and medications.

B) **Screening at each study visit:** Female subjects will be required to take a urine pregnancy test before each visit begins. A positive test at anytime will result in exclusion. A Modified Allen's test will be performed on Day 1 for all subjects and during day when an arterial line is placed (Day 3). Failing the Modified Allen's test at anytime will result in exclusion.

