
Men and women aged 18-40 recruited from subjects in the surrounding community, as well as individuals who have previously participated in research studies in the Cardiopulmonary and Respiratory Physiology Lab at the University of Oregon who are known to have/not have a PFO. Specifically, we are looking to recruit 6 male and 9 female subjects, have them fully participate in the study, and then we will be able to appropriately analyze the effect of biological sex on our outcome variables. It may be the case where we end up recruiting more subjects, if for example other exclusionary criteria are met.
	
Previous history of coronary artery disease (ischemic heart disease such as angina, heart attack, myocardial infarction). Failure of Modified Allen's Test in both hands. Currently taking medications or herbal supplements for any heart or respiratory disease that they cannot stop taking for 48hrs prior to testing (seasonal allergy medication not included in exclusion medications). Lidocaine, nitroglycerine or heparin allergy. Women who are pregnant or trying to become pregnant. Previous history of any condition that would prevent the subject from performing cycle ergometer exercise (for exercise study only). Because we are looking to recruit enough male (6) and female (9) subjects to fill in data from our preliminary work, if (for example) we reach the point where we have recruited and studied 9 female subjects, the next female who may be interested in participating may end up being excluded. This is to ensure we have an even number of male/female subjects to appropriately test the potential effect of biological sex on our outcome measures. Recreational drug use.

Compensation

Subject Compensation (maximum of \$220):

Visit #1: \$25: Completing the informed consent and health history questionnaire (\$5.00) and echocardiographic screening and blood draw (\$10.00) will pay \$15.00 total. The pulmonary function tests, the diffusion capacity test, and the whole body plethysmography or nitrogen washout will pay \$10.00. Subjects who choose not to participate upon review of the informed consent or are excluded based on any findings during this visit will be paid for their degree of visit completion.

Visit #2: \$20: Completing the six minute walk test (\$5) completing the VO2max test (\$15).

Visit #3: \$175: Completing the arterial blood line (\$100) and exercise tests (\$75).

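### The plan predicts no sex effect on gas exchange but only tests for a difference, with no margin or interval rule, so no planned result could support that prediction

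*Combined protocol and SAP*

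**What the plan says.** Section B (Hypotheses) puts two predictions about gas exchange in one sentence: a large PFO will make it worse, "compared to those with a small or no PFO; there will not be a sex effect". 

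Section D (Sample Size and Data Analyses) holds the whole analysis plan. It begins "Mean differences in AaDO₂ and core body temperature between males and females, and between those with a small or no PFO" and assigns these outcomes to a mixed analysis of covariance. VO2max, six-minute walk and inflammatory markers get unpaired t-tests. The same section says that "n = 15 individuals would be sufficient to test our hypotheses", then asks for 45 subjects.

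Sex is a stated purpose of the study. Section A says "we would like to build on this work by examining the potential effect of biological sex". Table 1 sets recruitment at 6 men and 9 women, after which "then we will be able to appropriately analyze the effect of biological sex on our outcome variables". It describes these subjects as additions to an existing set: "Because we are looking to recruit enough male (6) and female (9) subjects to fill in data from our preliminary work". The size and sex mix of that set are not given.

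No section gives an equivalence margin, an equivalence test, a confidence-interval rule or a definition of a negligible sex difference. Nor does any section say how a non-significant sex result will be read.

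**The concern.** The sex hypothesis asserts an absence, but the planned analysis is built to detect a presence. A significant result would count against the hypothesis. A non-significant one would not count for it, because it is the expected result both when the sexes do not differ and when they differ but the sample is too small to show it. The plan has no third outcome.

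The recruits are chosen by sex so that this question can be answered, and further women may be turned away once nine have been studied. Without a criterion for support, the likely report is that no sex effect was found, and readers may take that as evidence that men and women are alike. At the sample sizes the documents suggest, it would not be.

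**Working it through.** **The plan's own figure.** The n = 15 cannot be reproduced. Section D cites a power program and a physiologically meaningful effect, but gives no alpha, sidedness, power, effect size or SD, and does not say whether 15 is a total or a group size. Solving backwards for the difference detectable with 80% power at two-sided 5% (two-sample t-test) gives 1.57 SD if 15 is the total (7 vs 8) and 1.06 SD if it is 15 per group. For comparison, 6 vs 9 gives 1.60 SD and 22 vs 23 gives 0.85 SD. The finding does not depend on which reading is right.

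**Inputs.** The counts 6 and 9 are from Table 1, and the total of 45 is from section D. Assumed, because the documents do not give them: two-sided 5%, one between-subject comparison with equal SDs, differences in SD units, and even splits of 30 (15 vs 15) and 45 (22 vs 23).

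**Precision.** The 95% interval half-width is t(0.975, n1+n2−2) × √(1/n1 + 1/n2), in SD units:

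- 6 vs 9: 2.160 × 0.527 = 1.14
- 15 vs 15: 2.048 × 0.365 = 0.75
- 22 vs 23: 2.017 × 0.298 = 0.60

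**Chance of a non-significant result.** This is 1 minus the power of the t-test, from the noncentral t distribution with noncentrality d / √(1/n1 + 1/n2). For d = 0.5 the noncentrality is 0.95, 1.37 and 1.68 for the three splits.

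| True sex difference | 6 vs 9 (new recruits only) | 15 vs 15 | 22 vs 23 |
|---|---|---|---|
| 0 | 95% | 95% | 95% |
| 0.5 SD | 86% | 74% | 63% |
| 0.8 SD | 71% | 44% | 25% |
| 1.0 SD | 58% | 25% | 9% |

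With 22 vs 23, a true difference of 0.5 SD would still be missed more often than found.

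**What a no-effect claim would need.** An equivalence claim at margin M succeeds when the 90% confidence interval lies wholly inside ±M (two one-sided tests at 5% each). The probabilities below assume a true difference of zero and were obtained by integrating over the distribution of the sample SD. Two of them were checked by simulation with 200,000 runs and agreed to within 0.001.

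| Margin (assumed) | 6 vs 9 | 15 vs 15 | 22 vs 23 | n per sex for 80% |
|---|---|---|---|---|
| 0.3 SD | 0% | 0% | 0% | 191 |
| 0.5 SD | 0% | 1% | 6% | 70 |
| 0.8 SD | 4% | 38% | 68% | 28 |
| 1.0 SD | 18% | 70% | 90% | 18 |

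The 6% at ±0.5 SD has a simple explanation. With 22 vs 23 the 90% half-width is 1.681 × 0.298 = 0.50 SD, so the interval fills the margin even when centred on zero.

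**The case against.** The strongest reply is that no error has yet been made. Nowhere do the documents say that p>0.05 will be taken as proof of no sex effect. The clause in section B can be read as a physiologist's expectation, which a difference test can refute, and the named models can yield an estimate and interval for sex without any design change. All of that is true, and it makes the remedy cheap. It does not remove the gap, because section D says the sample suffices to test the hypotheses and this is one of them. No rule says what would count in its favour.

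Three narrower points have some force.

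- The 6 vs 9 comparison is probably not the final analysis set, since those subjects are meant to supplement earlier data and balance the sexes. The conclusion should therefore rest on the larger splits, where the problem remains. With 22 vs 23 the test is fairly informative about differences of 1.0 SD, missing them only 9% of the time.
- A sex effect could mean a main effect or a modification of the PFO-size effect. The figures above cover only the main effect. An interaction would normally be estimated less precisely, so that reading does not help the plan.
- Repeated workloads, covariates or pooled preliminary data could improve precision. The documents give no figures for any of these, and better precision would still not supply the missing criterion.

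The uncertain analysis sample size is a separate omission. It affects how large the problem is, not whether it exists.

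**Conclusion.** The concern holds. As written, the plan can contradict the hypothesis of no sex effect but has no outcome that could support it. This follows from the text alone and does not depend on the sample size.

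The practical size of the problem depends on the assumptions listed: a single two-group comparison, two-sided 5%, equal SDs, assumed effect sizes, and assumed even splits of 30 and 45. On those terms a non-significant result is compatible with moderate sex differences at every sample size considered, and with large ones at the smaller sizes. About 45 subjects would give 80% power for an equivalence claim only at margins of roughly 0.9 SD or wider. The PFO-size comparison is not affected.

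**What to change.** **Preferred change.** In section B, replace the no-effect prediction with an aim to estimate the effect of sex, which matches the stated intent in section A. In section D, add that the sex main effect and the sex-by-PFO interaction for AaDO2 will be reported as estimates with 95% confidence intervals, and that absence of a sex effect will not be concluded from p>0.05. State how many preliminary subjects, by sex, enter the analysis. The cost is one reworded clause and one or two sentences. The drawback is that the sex question may have to be reported as inconclusive.

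**If a no-effect claim is kept.** Pre-specify an AaDO2 margin in mmHg with its physiological justification. Make the claim only if the 90% confidence interval lies inside that margin, and otherwise report the sex effect as unresolved. This may become a sample-size problem. Under the assumptions above and no true difference, a margin of ±0.5 SD needs about 70 per sex for 80% power, while ±1.0 SD needs about 18 per sex. The margin is for the investigators to choose and should be fixed before the data are analysed.

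### The planned t-tests cannot show whether PFO size matters in each sex and leave the PFO comparison unadjusted for sex; the mixed ANCOVA does not state a sex-by-PFO term

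*Combined protocol and SAP*

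**What the plan says.** The title is "Does Patent Foramen Ovale Size Matter in Men and Women". The goal in section B is to "examine how cardiopulmonary and respiratory physiology may be altered by the size of a PFO and/or biological sex". Section A treats sex as a further question: "in addition to the potential size effect on our outcome measures, we would like to build on this work by examining the potential effect of" (the sentence ends by naming sex). The hypotheses add that "there will not be a sex effect", without saying whether this means the average male-female difference or a difference in the PFO effect between the sexes.

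Table 1 sets recruitment at 6 men and 9 women, to complete data from preliminary work and even out the sexes. Once a sex target is met, further volunteers of that sex may be turned away. Sample Size and Data Analyses derives n = 15 and requests 45.

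The same section names two contrasts, in almost the same words, for two sets of outcomes: mean differences "between males and females, and between those with a small or no PFO compared to a large PFO will be analyzed". For AaDO2 and core temperature the method is a mixed analysis of covariance whose factors, covariates and interactions are not listed. For VO2max, six-minute walk and inflammatory markers it is an unpaired t-test. VO2max and TNF-alpha are among the variables that the section calls primary. The text mentions no sex-by-PFO term and no PFO comparison within each sex.

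**The concern.** A male-female comparison shows whether men and women differ in, say, VO2max. A large versus small-or-no PFO comparison shows an average PFO difference over whatever mix of men and women is enrolled. Neither says whether PFO size matters in men, in women, or in both.

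For the t-test outcomes there are two consequences. First, the by-sex question cannot be answered from the tests listed. Second, each test ignores the other factor. In the PFO comparison, any sex difference in the outcome goes into the error term, and it biases the comparison if the PFO groups differ in sex mix. The plan does not say that PFO groups will be balanced within sex.

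Because the hypothesis is one of no sex effect, a non-significant male-female t-test could be taken as confirming it, although that test says nothing about whether the PFO effect differs by sex.

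**Working it through.** **The plan's own figure.** n = 15 cannot be reproduced: no effect size, SD, alpha, power or test is given. Assuming two-sided 0.05 and 80% power, it would imply a standardised difference of 1.57 if 15 is the total (7 v 8), or 1.06 if it is per group. The point does not depend on which.

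**Inputs.** From the documents: 6 men and 9 women (Table 1) and 45 requested (Sample Size and Data Analyses). Assumed: the PFO split within each sex, effects in SD units, two-sided 0.05 and 80% power. The number of preliminary subjects to be combined with the new recruits is not given, so I show 15 and 45.

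**1. Dilution of a one-sex effect.** If the PFO split is the same in both sexes, the pooled PFO contrast equals the effect times the share of the affected sex.
- Equal sexes: 0.5 of the effect.
- 6 men and 9 women, effect in women only: 9/15 = 0.6.
- 6 men and 9 women, effect in men only: 6/15 = 0.4.

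**2. Bias and noise from ignoring sex.** Let G be the male-female difference in the outcome.
- Bias in the PFO contrast = (share of men in the large group − share of men in the small-or-no group) × G. As an illustration, with 4 men of 7 in one group and 2 of 8 in the other (still 6 men and 9 women), the bias is (0.571 − 0.250) × G = 0.32G.
- Even with equal sex mix, the within-group variance rises by p(1 − p)G². With p = 6/15 this is 0.24G²; for G = 1 SD the error SD becomes √1.24 = 1.11 SD.

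**3. Precision of the proposed estimates.** SE(interaction) = SD × √(sum of 1/n over the four cells). The equally weighted average of the two within-sex effects has half that SE. For AaDO2 and core temperature this applies to a single value or average per subject.

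| Assumed cells (men large, men small/no, women large, women small/no) | Interaction SE | Main-effect SE |
|---|---|---|
| 11/11/11/12 (N = 45) | √(3/11 + 1/12) = 0.60 SD | 0.30 SD |
| 7.5/15/7.5/15 (N = 45, one third large) | √(2/7.5 + 2/15) = 0.63 SD | 0.32 SD |
| 3/3/4/5 (N = 15) | √(2/3 + 1/4 + 1/5) = 1.06 SD | 0.53 SD |
| 2/4/3/6 (N = 15, one third large) | √(1/2 + 1/4 + 1/3 + 1/6) = 1.12 SD | 0.56 SD |

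Within-sex SEs are √(1/11 + 1/11) = 0.43 and √(1/11 + 1/12) = 0.42 SD at N = 45 (first row), and √(1/3 + 1/3) = 0.82 SD (men) and √(1/4 + 1/5) = 0.67 SD (women) at N = 15 (third row).

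**4. What could be detected.** These figures use the noncentral t, fractional cells, and PFO splits of 1:1 and 1:2.
- Detectable at 80% power with N = 45: 0.85–0.91 SD for the PFO main effect and 1.71–1.81 SD for the interaction.
- Detectable at 80% power with 6 men and 9 women: 1.57–1.66 SD and 3.24–3.44 SD.
- A 1.0 SD effect in women only, N = 45 with equal sexes: the pooled contrast sees 0.50 SD and has 34–37% power, the interaction also 34–37%, and a women-only comparison 57–62%. The pooled figure is slightly generous, because it ignores the extra spread when affected and unaffected subjects share the large-PFO group.

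**The case against.** The strongest reply is that the plan does what its aims say. The title can be read as asking about PFO size in a mixed-sex sample. The goal speaks of size and/or sex, the background treats sex as an additional question, and no aim or hypothesis states that the PFO effect differs by sex. Two main-effect contrasts fit that reading. This stands: a reader might infer that the plan fails a declared interaction aim, and the documents do not support that. The mismatch is with the by-sex reading of the title. The failure to adjust the PFO t-tests for sex does not depend on how the title is read.

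A second reply is that the mixed ANCOVA may already contain a sex-by-PFO term. That also stands. A reader might infer that the interaction is excluded for AaDO2 and core temperature, but it is only unspecified. It does not help the t-test outcomes, because a single-factor two-group test has no place for the term.

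A third reply is that the interaction will be too imprecise to change conclusions. The imprecision is real (step 4). It is a reason to report intervals and claim little, and not a reason to leave the by-sex question to tests that cannot address it. Adjustment for sex is useful whatever the interaction's precision.

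**Conclusion.** The concern holds for VO2max, six-minute walk and inflammatory markers: the listed tests cannot yield a PFO-size effect by sex, and their PFO comparison ignores sex. For AaDO2 and core temperature it is a gap in prespecification only. The change is worth making, and it does not invalidate the study.

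An effect confined to one sex could be missed, or could be reported for both sexes at about half its size (0.4 or 0.6 of it with 6 men and 9 women and equal PFO splits). A reader might infer that such an effect would always be reported as an average in both sexes. That goes too far: for a 1.0 SD women-only effect at N = 45, the pooled test would more often miss it than find it.

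A reader might also infer that the study was widened to both sexes in order to examine sex. Section A says only that the earlier work could not recruit equal numbers of each.

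The sizes rest on assumed PFO splits, SD-unit effects and two-sided 0.05. The structural point rests on none of these.

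**What to change.** - For VO2max, six-minute walk and each inflammatory marker, replace the separate t-tests with one linear model containing sex, PFO group (large v small or none) and sex-by-PFO group.
- For AaDO2 and core temperature, state the same between-subject terms in the mixed ANCOVA.
- For each outcome, report with 95% confidence intervals the PFO-size effect overall (adjusted for sex), in men and in women, and the interaction.
- Label the within-sex and interaction results as estimation, and state that a non-significant result will not be reported as showing no difference by sex.
- Report the number of subjects in each of the four sex-by-PFO cells.

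The cost is a change of analysis wording, a few more table columns and two more degrees of freedom than a t-test uses. No new subjects, visits or measurements are needed. The downside is wide intervals. With the near-equal cells above, the 95% half-width for the interaction is about 2.02 × 0.60 = 1.2 SD at N = 45 (41 df) and 2.20 × 1.06 = 2.3 SD at N = 15 (11 df).

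### VO2max, six-minute walk and inflammatory markers get separate unpaired t-tests for sex and for PFO size, so the PFO comparison is not adjusted for sex and a PFO × sex interaction cannot be estimated

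*Combined protocol and SAP*

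**What the plan says.** The overarching goal (section B) is to learn how "physiology may be altered by the size of a PFO and/or biological sex", and the title asks the question in men and women.

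Sample Size and Data Analyses (section D) splits the outcomes in two. AaDO2 and core temperature go to a mixed analysis of covariance, whose factors and covariates are not listed. VO2max, "6 minute walk test, inflammatory markers between males and females, and between those with a small or no PFO compared to a large PFO", go to a simpler method: the sentence ends "compared to a large PFO will be analyzed using an unpaired t-test". The same section names VO2max and TNF-alpha among the primary outcome variables.

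On sex balance, section A says of the preliminary work that "due to logistical constraints, we were unable to recruit an equal number of female and male subjects". Table 1 plans 6 men and 9 women to complete those data and says "This is to ensure we have an even number of male/female subjects". Section D asks for 45 subjects and allows sex to be chosen so that the distribution is even. The supplied text gives no sex split within the PFO-size groups, and no covariate, stratified analysis or two-factor model for the t-tested outcomes.

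**The concern.** The study has two factors, and for these outcomes the plan looks at one at a time. An unpaired t-test on PFO size cannot hold sex constant and has no term for whether the PFO effect differs between men and women.

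For any outcome that differs by sex, this has two consequences:

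- **Similar sex mix in the two PFO groups.** The sex variance stays in the error term and widens the interval for the PFO effect.
- **Different sex mix.** The PFO difference also absorbs part of the sex difference. Even totals do not prevent this, because PFO size is observed rather than assigned and balance is promised only overall.

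Two primary outcomes are affected, while AaDO2 and core temperature get a model that could carry both factors. Where an outcome does not differ by sex, little is lost either way.

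**Working it through.** **The plan's own figure.** Section D calls n = 15 sufficient. It cannot be reproduced, because effect size, SD, alpha, sidedness and power are not given, nor whether 15 is per group or in total. At two-sided 5% and 80% power (assumed), 15 per group corresponds to a standardised difference of 1.06. A total of 15 corresponds to 1.57 (7 against 8) to 1.66 (5 against 10).

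**Inputs.** From the documents: 45 subjects and the two contrasts. Assumed: 22 men and 23 women; 15 large against 30 small or no PFO; normal outcomes with within-sex SD 1; true PFO effect δ = −0.9 SD (the t-test detects about 0.906 at 80% power with 15 against 30); sex gap γ (men minus women) of 0, 0.5, 1.0 and 1.5 SD; two-sided 5%.

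**Formulas.** With p_L and p_S the male proportions in the large and small/no groups, the t-test estimates

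δ + (p_L − p_S) × γ.

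Its within-group SD is about √(1 + γ² p(1 − p)), and its 95% half-width is about 2.017 × √(1/15 + 1/30) × SD = 0.638 × SD. With sex in the model the SD stays at 1.

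**1. Similar mix (7M/8F against 15M/15F), p about 0.5.** At γ = 1.0 the SD is √1.25 = 1.118 and the half-width is 0.638 × 1.118 = 0.71. At γ = 1.5 the SD is √1.5625 = 1.25 and the half-width is 0.638 × 1.25 = 0.80. Adjusted, it is 0.64.

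**2. Averaged over chance mixes.** If sex is unrelated to PFO size, the number of men in the large group is hypergeometric (45 subjects, 22 men, 15 drawn).

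**3. Tail mix, 5M/10F against 17M/13F, no PFO effect.** p_L − p_S = 5/15 − 17/30 = −0.233, so the spurious difference is −0.12, −0.23 and −0.35 SD at gaps of 0.5, 1.0 and 1.5.

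**4. Opposite tail, 10M/5F against 12M/18F, δ = −0.9.** p_L − p_S = 10/15 − 12/30 = 0.267, so the bias is 0.13, 0.27 and 0.40 SD and the estimate is −0.77, −0.63 and −0.50.

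Simulated rejection rates (60,000 replicates per fixed mix; 20,000 per mix for the averages):

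| Scenario | γ = 0 | 0.5 | 1.0 | 1.5 | With sex in the model |
|---|---|---|---|---|---|
| 1. Similar mix, t-test power | 80% | 79% | 75% | 68% | 79–80% |
| 2. Chance mixes, t-test power | 79% | 77% | 70% | 60% | 78–79% |
| 2. Chance mixes, t-test type I error | 5.0% | 5.0% | 5.1% | 5.0% | 5% |
| 3. Tail, t-test type I error | 5% | 5.8% | 7.4% | 8.5% | 5% |
| 4. Opposite tail, t-test power | 79% | 64% | 41% | 19% | 77% |

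Repeat runs agreed to within about half a point; the 8.5% came out at 8.8%.

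**How often the tails arise.** P(5 or fewer men among the 15) = 0.123 and P(10 or more) = 0.085, together 0.208.

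**Interaction.** For 7/8 against 15/15 the standard error is √(1/7 + 1/8 + 1/15 + 1/15) = 0.633 SD. With t(0.975, 41) = 2.02, the half-width is 1.28 SD.

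**The case against.** **Sex is already controlled through recruitment, and the t-test is valid on average.** If sex is unrelated to PFO size, type I error averaged over chance mixes is about 5%, and nothing in the documents links large PFO to sex. The typical cost is therefore precision, not false positives. This stands. Scenarios 3 and 4 are tails, and the 19% needs both an 8.5% tail and the largest assumed sex gap. But the study will have one realised mix, and the plan has no step to correct it.

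**The interaction is not a stated hypothesis.** This is true. The only sex prediction is "there will not be a sex effect", placed beside gas exchange. A half-width of about 1.3 SD exceeds the 0.9 SD effect assumed here, so the estimate would be imprecise. The missing adjustment is the firmer half of the point, and the interaction belongs in a secondary role. It is the planned test that cannot estimate it, not the data.

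**The inputs are assumed.** This is also true, apart from the 45. At a sex gap of 0.5 SD with a similar mix, the loss is negligible. The plan does not say whether VO2max is scaled to body mass, so its sex gap cannot be inferred.

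**A different PFO split can remove the loss.** For 22 against 23, a mix of 11M/11F against 11M/12F gives t-test power of 75% to 64% at gaps of 1.0 to 1.5, against 84% adjusted. A mix of 10M/12F against 12M/11F gives 83% to 79%. In that second case the power is held up by bias, since the estimate drifts from −0.90 to −0.97 and −1.00. No single value describes this split.

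**The analysed number is unsettled.** Section D asks for 45, while Table 1 recruits 15 to add to earlier data. At 15 (3M/4F against 3M/5F), power for 0.9 SD is only about 36% even with sex in the model. Adjustment does not rescue a sample that small.

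**Conclusion.** The concern holds. For VO2max, six-minute walk and the inflammatory markers, the planned analysis neither adjusts the PFO comparison for sex nor estimates a PFO × sex interaction, and nothing elsewhere in the supplied text fills the gap.

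The expected cost is lost precision: under the assumptions above, roughly 9 points of power at a sex gap of 1.0 SD and 18 to 19 points at 1.5 SD, averaged over chance mixes. At no gap the cost is nil, and at 0.5 SD it is 1 to 2 points. The less likely cost is bias in an unbalanced realised mix: 0.23 to 0.40 SD at gaps of 1.0 to 1.5 in the two tail cases. Mixes at least that extreme in the large group arise about 21% of the time if sex and PFO size are unrelated.

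The plan should be changed, because the remedy is cheap and two primary outcomes are affected. The design itself is not undermined.

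**What to change.** For VO2max, six-minute walk distance and each inflammatory marker, replace the two t-tests with one linear model containing PFO group (large against small or no) and sex.

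- Report the sex-adjusted PFO difference with its 95% CI as the main result, and the sex difference with its 95% CI from the same model.
- Report the PFO × sex interaction from a secondary model as an estimate with its 95% CI, not as a pass/fail test. State in advance that the expected half-width is about 1.3 SD at 45 subjects.
- Tabulate sex by PFO group, so the reader can see the realised mix.

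Separately, the prediction of no sex effect concerns gas exchange. Report the sex difference in AaDO2 with its 95% CI, and do not read a non-significant test as evidence of no difference.

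**Cost.** Only analysis wording changes; sex and PFO grade are already collected. The main model uses one more degree of freedom than the t-test and the secondary model two. With no sex gap, power falls from 79.3% to 78.4%, averaged over chance mixes.
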